		6.4.5	Added section on Pre-screening via REDCap & telephon										
		0.4.5	surveys, and the emailing of materials to prospective participants										
		6.5	Clarified that travel stipends are only available for visits to the research clinic/Rachel Upjohn building										
			Added beta blockers and opioids and SNRIs to the list of										
		7.5/7.6	contraindicated meds										
			Added Beck Scale for Suicidal Ideation										
			Added Demographics form, Work & Social Adjustment										
		9.5/9.6	Form, fMRI screening form, and Treatment Expectation										
		,	and Satisfaction forms; Insomnia Severity Index;										
			Morningness/Eveningness Questionnaire										
		9.71	Added section on fMRI practice										
		9.7.4	Added section on Emotional Regulation Task										
			Clarified screening process for fMRI as relates to										
		9.9.1	pregnancy and drug screening										
		12.2.2/12.3.3.1	Indicated that video files will be stored on MBox										
		12.3.2	Added section naming the Independent Safety Monitor										
		12.4	Added ERT and WSAS to abbreviations list										
		13	Added references for BSSI and WSAS questionnaire										
			Added footnote to SOA and language to section 5.1 that										
1 42		1.3; 5.1	allows for Visit 2 activities to occur on two separate days.										
Jan. 13,	3.0		Updated incentive schedule to reflect possibility of										
2020		6.5	receiving an additional travel stipend related to visit 2										
			schedule										
Feb. 4,	4.0	6.2	Updated Exclusion Criteria to specify excluding for										
2020	4.0	0.2	significant light treatment use and/or use in the past year										

5.0	6.4.3; 6.4.4	Updated recruitment strategies to specify flyering at the VA and removed flyering at the VA as a future									
		recruitment strategy.									
		Updated SOA to indicate that the PCL-5 and DASS will									
6.0	1.3	also be collected at lab visits 4 and 6; updated Table of									
		Contents									
7.0	3.1.5.1	Removed language that indicated only the clinician would be filmed.									
7.0	6.5	Outlined additional travel stipend amount depending on									
	0.5	distance which participant will be traveling to the lab.									
8.0	6.4.3	Updated to reflect that IRB approved study fliers will be									
10, 2020		posted on Wayne State University campus.									
October 9.0 13, 2020		Added drug test to lab visit 2									
		ALL LD . D: ./FMFDCF									

1 PROTOCOL SUMMARY

1.1 SYNOPSIS

Title:	Morning Light Treatment for Traumatic Stress: The Role of Amygdala Reactivity
Study Description:	Participants will be enrolled in a 3-arm randomized controlled trial of a 4-week self-administered wearable morning light treatment to evaluate the dose-response association between amount of light therapy (15, 30 or 60 minutes per day) and the degree of brain reactivity in the amygdala in response to an emotional faces fMRI task.
Primary Objective	Average blood-oxygen-level-dependent (BOLD) percent signal change in the bilateral amygdala from baseline to week 2 and/or baseline to week 4 of treatment.
Study Population:	Individuals with traumatic stress and significant distressing symptoms
Phase:	n/a
Description of Sites/Facilities Enrolling Participants:	University of Michigan Sleep and Circadian Research Lab & North Campus fMRI suite
Description of Study Intervention:	Daily self-administered morning light therapy delivered using a commercially available device, the Re-Timer.
Study Duration:	3 years
Participant Duration:	5 weeks

1.2 SCHEMA

The figure below shows a sample protocol for an individual whose average sleep schedule is 12-8am:

1.3 SCHEDULE OF ACTIVITIES

Study Phase	Screening & Baseline 5																					I	nterv	entio	n												
Day Number 1							6	10	11	12	13	14	15	16	17	18	19	20	21	22	23	24	25	26	27	28	29	30	31	32	33	34	35	36			
Visit Number	٧1	v2 ⁶							٧3							٧4							٧5							9^							٧٧
Informed consent	Х																																				
Eligibility Confirmation	Х	х																																			
Vision Testing	Х																																				
Psychological assessment		Х																																			
Accelerometry		Χ	Χ	Χ	Х	Х	Х	Х	Х	Χ	Χ	Х	Х	Χ	Х	Х	Х	Х	Χ	Χ	Χ	Х	Х	Χ	Χ	Χ	Χ	Χ	Х	Х	Χ	Χ	Χ	Χ	Χ	Х	Χ
PSQI									Х														Х														Χ
Daily log ²		Х	Х	Х	Х	Х	Х	Х	Х	Χ	Х	Х	Х	Х	Х	Х	Х	Х	Х	Χ	Χ	Х	Х	Х	Χ	Χ	Χ	Χ	Х	Х	Χ	Χ	Χ	Х	Х	Х	Χ
Urine screen ³	Х	х							Х														Х														Χ
Breathalyzer	Х	Х							Х							Х							Х							Х							Χ
Clinician-administered assessments									х														Х														Х
Self-report questionnaires									Х							X ⁷							Х							X ⁷							Х
fMRI ⁴									Х																												Χ
Randomization									Х																												
Treatment expectation									Х																												
Light therapy										Χ	Х	Х	Х	Х	Х	Х	Х	Х	Х	Х	Х	Х	Х	Х	Х	Χ	Х	Χ	Х	Х	Χ	Χ	Х	Х	Х	Х	Х
Treatment fidelity – daily contact										Х	Х	х	х	Х	х	Х	х	х	Х	Х	Х	Х	Х	Х	Х	Х	Х	Х	х	х	Х	Х	Х	Х	Х	Х	Х
Treatment fidelity – data download & feedback																х							х							х							Х
AE Assessment (SAFTEE/CSSRS)	х	х							Х							Х							Х							Х							Х
Treatment satisfaction																																					Χ

^{1 –} Exact day number can vary by up to one week; 2 – Daily log will capture information about sleep time, treatment time, medication use, etc.; 3 – Urine drug screen administered via dipstick by study team at baseline and urine pregnancy screen to ensure drug free participants; 4 – fMRI must occur within 7 days of clinician-administered assessments; 5 – Final screening and eligibility confirmation occur on day 0/v1 and the start of the weeklong baseline period begins at v2; 6 – Visit 2 activities may be split across 2 days separated by no more than 1 month; 7 – Only the PCL-5 and DASS will be administered at these visits

2 Introduction

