5 STUDY DESIGN

5.1 OVERALL DESIGN

- Single-blinded randomized controlled mechanistic trial
- Parallel groups
- 3 study arms based on light treatment duration: 15-minutes, 30-minutes or 60-minutes/day
- 4-weeks of morning bright light treatment delivered via Re-Timer device

This is a 5-week study (1-week of baseline and 4-weeks of intervention) that includes a screening visit plus 6 additional study visits to evaluate outcomes and monitor progress. Potential participants are prescreened for major exclusion criteria using a combination of online and telephone surveys. On Day 0 (Visit 1) individuals are consented and eligibility confirmed using several self-report questionnaires. Final eligibility is confirmed after the clinician interviews on visit 2 do not reveal any exclusionary psychiatric conditions (see below).

Participants return to the lab for study visit 2 for a battery of psychological assessments to characterize the sample, and to begin the week-long baseline period (see Section 1.3 - Schedule of Activities). At this visit, participants are provided with their study materials (Actiwatch Spectrum, daily log, instructions to sleep according to a normal schedule, etc.). To minimize burden participant burden and to accommodate calendar challenges (e.g. time change), the activities for this visit may be split across 2 days such that the psychological assessments are done on one day and the distribution and training of study materials occur on a second day within 1 months' time.

On Day 8 (Visit 3) participants return to the lab for randomization and baseline outcome assessments. Morning light treatment begins on the morning of Day 9. Thereafter, participants come to the research lab weekly to assess adherence to the study procedures and intervention, and monitor for side effects. Outcome assessments occur on Day 8, Day 22 (week 2 of intervention) and Day 36 (week 4 of intervention). The exact day number of study visits and activities can vary by up to a week; and we will try to schedule study visits for the same time of day. While the plan is to schedule the fMRI for the same day as the psychological assessments, we do allow for a 7-day window in cases where same-day scheduling is not possible.

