9.4 SLEEP ASSESSMENT

We will assess sleep using both objective (actigraphy) and subjective (PSQI) measures to use as compliance indices and covariates. Daily logbooks will supplement these assessments, and are designed to capture wake/bed times, treatment times, etc.

- Wrist actigraphy using the Actigraph Spectrum every day for duration of study
- Daily Logs
- Pittsburgh Sleep Quality Index (PSQI) [95]
- Morning-ness & Eveningness (Owl-Lark) Questionnaire [135]
- Insomnia Severity Index (ISI) [136]

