9.7 FMRI

Amygdala reactivity will be measured using fMRI and change in BOLD signal measures across the study period. Images will be acquired using an Echo-Planar Imaging sequence (TR=800 ms, FOV=23, slice=2.4mm, 96x96 matrix) to measure brain function at rest and during the EFAT task, optimized to reduce susceptibility artifact. fMRIs (initially at visits 3, 5 and 7 but later changed to only visits 3 and 7) will be scheduled at the North Campus facility and must occur within 7 days of the clinician-administered and self-reported assessments of trauma stress and mood (see Section 9.3)

9.7.1 fMRI Practice

As part of the screening process, individuals will be able to lie in the mock scanner located at the Rachel Upjohn Building. This scanner is built to size, and includes simulating scanner noise from speakers so people can hear the noises associated with scanning.

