11.3.3 Baseline Analysis and Covariate Adjustment

With minimization randomization, we do not expect groups differences in the distributions of potentially prognostic baseline variables. We will check for imbalances in other baseline variables not used in minimization including childhood trauma and objective measures of total sleep time (sleep duration), wake after sleep onset (sleep continuity) and sleep quality (PSQI) assessed prior to baseline and include them as covariates in the analyses as needed. To explore how much of the change in amygdala reactivity and traumatic symptom reductions are associated with an improvement in sleep, we will also include separately each potential intermediate outcomes of the weekly average of total sleep time, wake after sleep onset and sleep quality assessed prior to each study visit (Days 22, 36) as predictors of outcomes. We will also explore if diagnostic status (baseline SCID) moderates the treatment response.

12 Supporting Documentation & Oversight Considerations

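### The exploratory sleep analysis takes the week before the study visit, but the scan may be up to 7 days from that visit, so off-day scans are paired with a misaligned sleep week.

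*Combined protocol and SAP*

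**What the plan says.** Section 11.3.3 states the aim of the sleep analysis: "To explore how much of the change in amygdala reactivity and traumatic symptom reductions are associated with an improvement in sleep". It calls the sleep variables intermediate outcomes and enters each one separately, using the "weekly average of total sleep time, wake after sleep onset and sleep quality assessed prior to each study visit (Days 22, 36) as predictors". One week, anchored to the visit, therefore serves both the amygdala and the symptom outcomes.

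The timing of the scan is set elsewhere. Footnote 4 in section 1.3 says "fMRI must occur within 7 days of clinician-administered assessments". Section 9.7 says that scans "must occur within 7 days of the clinician-administered and self-reported assessments of trauma stress and mood". Section 5.1 makes same-day scanning the plan and adds that "we do allow for a 7-day window in cases where same-day scheduling is not possible". None of the three says whether the scan may come before the visit, after it, or on either side. Section 6.5 has a stipend rule for scans held on a different day from the clinic visit, so off-day scans are foreseen.

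Scans were "initially at visits 3, 5 and 7 but later changed to only visits 3 and 7". Under section 9.4 wrist actigraphy is worn "every day for duration of study", and the schedule shows it to Day 36. The PSQI is scheduled at Visits 3, 5 and 7 only.

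**The concern.** An intermediate should be measured before the outcome it is meant to help explain. For the interviews and questionnaires, which take place at the visit, the week before the visit is the natural window. For the scan it fits only when scan and visit fall on the same day. Nothing in the plan moves the sleep week to the scan date, limits the window to one side, or sets off-day scans apart in this analysis.

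At stake is how to read the trial's planned look at whether better sleep accompanies a fall in amygdala reactivity. For an early scan, part of the predictor is sleep recorded after the scan, so an association could run in either direction. For a late scan, the most recent nights are missing from the predictor. A participant has one follow-up scan, or two if scanned before the Visit 5 scan was dropped, so there is little chance for misalignment to average out within a person.

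**Working it through.** The plan gives no figure on this point, so there is none to reproduce.

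**Inputs.** Sleep window: the week before the visit (11.3.3), taken as the 7 nights beginning on Days 29 to 35 and ending on the morning of Day 36. Scan window: up to 7 days from the assessments (1.3 footnote 4, 5.1, 9.7). Actigraphy: daily, scheduled to Day 36 (1.3, 9.4).

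**Early scan, on Day 36 − k.** A night beginning on Day d follows the scan if d ≥ 36 − k. Of Days 29 to 35, exactly k meet this, so the share after the scan is k/7.

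**Late scan, on Day 36 + k.** All 7 averaged nights precede the scan. The 7 nights just before the scan begin on Days 29 + k to 35 + k, so the averaged week contains 7 − k of them and leaves out k.

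| k (days) | Early scan: averaged nights after the scan | Late scan: nights just before the scan left out |
|---|---|---|
| 0 | 0/7 | 0/7 |
| 1 | 1/7 (14%) | 1/7 |
| 3 | 3/7 (43%) | 3/7 |
| 5 | 5/7 (71%) | 5/7 |
| 7 | 7/7 (100%) | 7/7 |

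**Average over off-day scans (assumption: spread evenly over 1 to 7 days).** If all are early, the mean share of averaged nights after the scan is (1 + 2 + … + 7)/(7 × 7) = 28/49 = 57%. If half are early it is 29%, and if none are it is 0%. The documents give neither the number nor the direction of off-day scans.

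**How different the two weeks might be (illustration only).** Assume nightly sleep is a stable personal level with variance s, plus an AR(1) part with variance 1 and parameter φ, plus independent noise with variance 1. The covariance of two 7-night means k nights apart is (1/49) ΣᵢΣⱼ [φ^|i − j − k| + s + 1(i − j = k)]. Dividing by its value at k = 0 gives the correlation.

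- s = 0, φ from 0.7 to 0.97: 0.72 to 0.92 at 3 days, 0.20 to 0.75 at 7 days.
- s = 1, same φ: 0.89 to 0.96 at 3 days, 0.68 to 0.87 at 7 days.

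The result depends heavily on s and φ, and the documents inform neither.

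**Effect of re-anchoring.** With the 7 nights that end on the scan morning, no night follows the scan. Scheduled actigraphy covers this window in full for scans on Days 29 to 36. For a scan k days after Day 36, k of the 7 nights have no scheduled actigraphy (1 of 7 on Day 37, 7 of 7 on Day 43). A late scan after Visit 5 has no such gap, because actigraphy continues.

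**The case against.** The strongest reply is that this is an exception inside an exploratory analysis. Same-day scanning is the plan, the aim is worded as association, and no formal mediation estimate is promised. Sleep may also be stable enough from one week to the next that the choice of week matters little: section 6.3.2 asks participants to keep their usual sleep-wake pattern, and section 7.2 gives the same daily light for 4 weeks. If, for illustration, 10% of scans were 3 days off, the less favourable correlations above give an average factor of 0.9 + 0.1 × 0.72 = 0.97 to 0.9 + 0.1 × 0.92 = 0.99. All of this stands and keeps the point minor. It does not remove it, because section 11.3.3 states a definite window that does not fit an off-day scan.

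A reader might infer three stronger things that the documents do not support:

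- **That every off-day scan puts sleep after the outcome.** This is true only of scans before the visit. For later scans the order is preserved and only a gap arises.
- **That the sleep association is weakened by the correlations shown.** These rest on assumed models, and on the further assumption that only the 7 nights just before the scan matter. Influence of amygdala change on later sleep could also strengthen the observed association in early scans.
- **That the 7-day scan window is itself wrong.** Footnote 4 only permits the window. The gap is in 11.3.3, which takes no account of it.

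**Conclusion.** The point holds in limited form. Followed as written, section 11.3.3 pairs an off-day scan with a sleep week that does not end at the scan: k of 7 nights fall after the outcome if the scan is k days early, and the k nights just before it are omitted if it is k days late. These counts follow from the stated windows and need no assumption beyond taking the sleep week to end on the visit morning.

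The scope is narrow. It covers off-day scans only, mainly at Visit 7 now that the Visit 5 scan has been removed, and only the amygdala part of this analysis. The dose-response test in 11.2, the go/no-go criterion in 11.1.2 and symptom outcomes collected at the visit do not use this pairing. Without the number and direction of off-day scans, neither the size nor the net direction of any bias can be given. This is a desirable correction, not a threat to the trial's main conclusion.

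**What to change.** In section 11.3.3, tie each sleep average to the date of its own outcome:

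- **Amygdala outcomes:** average actigraphy total sleep time and wake after sleep onset over the 7 nights before the actual fMRI date.
- **Symptom outcomes:** average them over the 7 nights before the assessment.
- **Scans after Visit 7:** use the recorded nights closest before the scan and flag these participants.
- **Sensitivity analysis:** repeat the amygdala analysis in same-day scans only, and report how many scans were early, same-day and late.
- **PSQI:** it is given only at visits, so leave it anchored there, and read its result for early scans as association only.

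The cost is revised wording and a merge on scan date. No new data are needed for scans on or before the visit. The remaining weakness is incomplete actigraphy for scans after Visit 7, which the flag and the same-day analysis make visible but do not cure.

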2.1 STUDY RATIONALE & BACKGROUND

2.1.1 Traumatic Stress and the Need for Additional Treatment Strategies That Target Brain Mechanisms The mental health burden of trauma is costly for individuals and society [37]. Evidence from a national sample of U.S. adults using the DSM-5 criteria, showed that 89.7% of individuals had been exposed to a traumatic event, including 53.1% of individuals exposed to direct interpersonal violence victimization [38]. Trauma leads to a wide variety of mental health problems including posttraumatic stress disorder (PTSD), depression, anxiety, substance use, and suicidality [23, 24]. Although front-line psychotherapies and pharmacotherapies exist for traumatic stress, evidence suggests that many individuals fail to receive treatment, let alone a therapeutic dose [25-28]. Uptake of these treatments is poor for several reasons including stigma, avoidance, unpleasant side effects, and poor accessibility [29]. Moreover, a substantial proportion of affected individuals remain symptomatic despite treatment [30-32]. New treatments are needed for traumatic stress that can overcome these critical barriers to care while targeting the underlying biological mechanisms of the pathology.

One of the central brain regions implicated in traumatic stress is the amygdala [39, 40]. The amygdala plays a critical role in emotional memory and the acquisition of fear responses [41], which are intimately related to the clinical manifestation of traumatic stress symptoms. Research has shown increased amygdala function during exposure to traumatic reminders [42, 43], and amygdala hyperactivity to salient cues has been linked to traumatic stress symptoms including posttraumatic stress symptoms [11, 12], depressive symptoms [13], and anxiety symptoms [14]. In a rodent model of PTSD, deep brain stimulation of the amygdala (inhibits amygdala function) reduced PTSD-like behaviors, demonstrating a causal link between changes in amygdala function and PTSD-like behavior [19, 20]. There is currently an ongoing trial of deep brain stimulation of the amygdala in humans (NCT02091843) and a published case report from the first patient (treatment resistant to psychotherapy and pharmacotherapy) showed substantial clinical improvements [21]. These studies suggest that changes in amygdala function are causally linked to changes in PTSD-like / PTSD symptoms. Moreover, several studies have demonstrated decreased amygdala activation as a result of successful treatment of PTSD [15, 16], depression [41], and anxiety disorders [44]. Thus, decreasing amygdala reactivity appears to be a critical treatment target for traumatic stress.

2.1.2 The Potential of Morning Bright Light as A Novel Treatment for Traumatic Stress Morning bright light treatment has good potential as a novel, non-invasive, low risk treatment for trauma-related disturbances in mood and arousal. With depression, the most recent meta-analyses reveal that morning bright light yields medium treatment effect sizes in seasonal depression (d=0.54, [17]) and nonseasonal depression (d=0.62, [18]). Antidepressant effects became statistically significant as early as 2 weeks after the initiation of a daily morning bright light treatment [17, 18]. Few studies have examined morning bright light treatment for anxiety, but there are some indications of anxiolytic effects [34-36]. In terms of post-traumatic stress disorder (PTSD), a recently completed morning bright light treatment trial has reported positive effects versus placebo (clinical trial NCT00701064). We have also shown in a placebo-controlled pilot trial (n=13) that a 4-week wearable morning bright light

treatment (Re-Timer) for people with probable PTSD led to clinical improvements in PTSD symptoms. While bright light is associated with some side effects (headache, eyestrain, nausea, agitation [45]), these often spontaneously remit [45, 46], and patients rarely discontinue due to side effects [46]. Bright light devices (with UV filter) are considered safe with no changes in ophthalmologic exams observed after 6 years of daily use (in fall and winter months) [47].

Light Reaches the Amygdala via Direct and Indirect Pathways, Can Reduce Amygdala Reactivity The primary circadian photoreceptors in the eye are specialized cells known as intrinsically photosensitive retinal ganglion cells (ipRGCs) [48]. IpRGCs express melanopsin, a photopigment that can respond to light directly [49]. IpRGCs also receive inputs from the rods and cones through conventional retinal circuitries [50]. The combination of intrinsic (melanopsin) and extrinsic (rod and cone) inputs enable ipRGCs to signal a large dynamic range of light levels in the environment (by a factor of 10 billion; from dim starlight to bright sunlight) [51]. IpRGCs transmit the light signal to various brain targets, including the amygdala [2]. The light signal reaches the amygdala directly via the ipRGCs [2], and also indirectly via other brain targets such as the suprachiasmatic nuclei, which is the central circadian clock in the brain [2, 33]. During fMRI scans with cognitive tasks, the application of a light signal immediately led to greater amygdala activation [9]. This effect was considered independent from the ongoing cognitive brain activity [9]. There is only one study that has examined amygdala activity before and after a bright light treatment. In this study, 30 healthy male participants received a 3-week morning bright white light treatment (30 min/day) of varying intensity, from 100-11,000 lux. The brighter the white light, the greater the pre- to post-treatment reduction in amygdala reactivity observed during an emotional faces fMRI task [10]. Thus, there is compelling evidence to suggest morning bright light treatment may reduce traumatic stress by inducing a reduction in amygdala reactivity. Although the amygdala is just one part of a larger neural network involved in the pathophysiology of traumatic stress, current evidence supports the hypothesis that light treatment can reduce traumatic stress symptoms via direct effects on amygdala function. If so, potential synergies with treatments targeting other nodes in this network may amplify the impact of this work and the importance of this potentially novel, noninvasive and scalable treatment.

